## Efficacy Endpoints:

- Change from baseline in Hb
- Number of red blood cell (RBC) transfusions during study
- Change from baseline in absolute reticulocyte count
- Change from baseline in LDH
- Change from baseline in haptoglobin
- Change from baseline in indirect bilirubin
- APL-2 serum concentrations (and pharmacokinetic (PK) parameters as appropriate
- Change from baseline in Functional Assessment of Chronic Illness Therapy (FACIT) scale and the Linear Analog Scale Assessment scale (LASA) including energy level, ability to perform daily activity, and overall quality of life (QoL)

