## 5.3.1 Red Blood Cell (RBC) Transfusions

The absolute and change in number of RBC transfusions per month will be tabulated using descriptive statistics by randomized dose group, by cohort, by phase of the study (Baseline, Part A Core Study Phase and Part B Long Term Extension Phase) and over the whole on-treatment study parts (Part A and Part B combined).

Summary statistics will be presented by study phase as follows:

- Baseline:
  - Number of Transfusions and Units per month for the *n* subjects who had at least 1 infusion in the 365 days prior to first study dose
  - Number of Transfusions and Units per month for the N subjects in the dose group (i.e. all subjects in the dose group, regardless of receiving transfusions prior to enrollment)
- Post-Baseline Study Phases (Part A, Part B, Part A and B combined):
  - Number of Transfusions and Units per month for the *n* subjects who had at least 1 infusion in the respective phase
  - Number of Transfusions and Units per month for the N subjects in the dose group (i.e. all subjects in the dose group, regardless of receiving transfusions during the respective phase)
  - Change from Baseline of the Number of Transfusions and Units for the N subjects in the dose group (i.e. all subjects in the dose group, regardless of receiving transfusions during the respective phase)

Only whole blood and Packed Red Blood Cell (PRBC) transfusions will be included.

The number of RBC transfusions per month will be calculated for each part of the study as:

RBC transfusions per month

number of transfusion reported during study part \* 28 number of days in that part of study

The whole on-treatment study will be from first dose to last dose received. A similar calculation will be used for the number of units transfused per month.

The baseline number of transfusions per month will be calculated as number of transfusions reported on 12-month transfusion history /12.

All 12-month transfusion history and on study transfusion data will be listed by Cohort. A separate listing of the number of transfusions per month and number of units transfused per month for baseline, each part and over the whole on-treatment study parts will also be included.

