### 5.1.3 Demographics and Baseline Characteristics

The following demographics will be tabulated by cohort (Cohort 1 wAIHA / Cohort 2 CAD) using summary statistics for continuous parameters and frequency/percent for categorical parameters at Part A Core Study Phase Baseline for Safety/PP Analysis Set:

- Age
- Sex
- Race
- Ethnicity
- Baseline Height
- Baseline Weight
- Baseline BMI

The following baseline characteristics will be tabulated using summary statistics for continuous parameters and frequency/percent for categorical parameters as well:

Version 1.0

- Time since diagnosis of wAIHA or CAD
- CH50
- AH50
- Complement C3
- C3d Type I, Type II, Type III
- Reticulocytes
- Haptoglobin
- Hemoglobin
- Anaemia categories (Mild: Hemoglobin ≥ 10 / Moderate: 5 ≤ Hemoglobin < 10 / Severe: Hemoglobin < 8)

- Plasma Hemoglobin
- Direct Antiglobulin Test (Negative / Positive)
- Baseline Cold Agglutinins (< 1:32 / 1:128 / 1:256 / 1:512 / > 1:512)
- Anti-C3 Coombs (Negative / WKPOS / 1+POS / 2+POS / 3+POS / 4+POS)
- Number of Transfusions Per Month in 12 Months Prior to First Dose (derived as the number of Packed Red Blood Cell transfusions in the 365 days prior to first APL-2 dose\*365/28)

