#### 5.3.1 Packed Red Blood Cell (PRBC) Transfusions

## 5.3.1.1 Transfusions Per Month

PRBC Transfusions per month will be derived for Part A + B Baseline, Part A + B, Part B Baseline, and Part B as follows:

• Part A + B Baseline Transfusions Per Month =

# of transfusions in 365 days prior to first APL-2 dose\*28 365

• Part A + B Transfusions Per Month =

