#### 5.3.1.2 Units Per Month

PRBC units per month will be derived for Part A + B Baseline, Part A + B, Part B Baseline, and Part B as follows:

• Part A + B Baseline Units Per Month =

# of units in 365 days prior to first APL-2 dose\*28 365

• Part A + B Units Per Month =

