#### 5.3.1.4 Transfusions Summary Tables

The following tabular summaries will be prepared:

- Part A + B PRBC: Summary statistics will be prepared by Cohort (Cohort 1 wAIHA / Cohort 2 CAD) for the ITT Set and Per Protocol Set who have Part A + B Baseline or at least one post-Part A + B Baseline PRBC transfusion during Part A + B phase:
  - Part A + B Baseline Transfusions Per Month
  - Part A + B Transfusions Per Month
  - Part A + B Baseline Units Per Month
  - Part A + B Units Per Month
- Part B PRBC: Summary statistics will be prepared by Cohort (Cohort 1 wAIHA / Cohort 2 CAD) for the ITT Set and Per Protocol Set who have Part B Baseline or at least one post-Part B Baseline PRBC transfusion during Part B Phase:
  - o Part B Baseline Transfusions Per Month
  - o Part B Transfusions Per Month
  - o Part B Baseline Units Per Month
  - o Part B Units Per Month

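### The Part A SAP counts whole blood and packed cells as RBC transfusions; the Part B SAP derives its rates, units and table membership from packed cells only, without explanation

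*SAP*

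**What the plan says.** Protocol section 8.2 lists the endpoint as "Number of red blood cell (RBC) transfusions during study". Section 3.2.2 of each SAP repeats it in almost the same words. None of the three limits it to packed cells.

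The Part A SAP (April 2020), section 5.3.1, has an explicit product rule: "Only whole blood and Packed Red Blood Cell (PRBC) transfusions will be included". The rule covers baseline, Part A, Part B and the two parts combined.

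The Part B SAP (November 2022) retitles section 5.3.1 for packed cells and does not mention whole blood:

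- 5.3.1.1: "PRBC Transfusions per month will be derived for Part A + B Baseline, Part A + B, Part B Baseline, and Part B as follows".
- 5.3.1.2: "PRBC units per month will be derived for Part A + B Baseline, Part A + B, Part B Baseline, and Part B as follows".
- 5.3.1.4 restricts the Part A + B summary table to subjects with a baseline transfusion or "at least one post-Part A + B Baseline PRBC transfusion during Part A + B phase". The Part B table has a parallel rule.
- 5.1.3, baseline characteristic: "derived as the number of Packed Red Blood Cell transfusions in the 365 days prior to first APL-2 dose".

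Section 5.3.1.3 of the Part B SAP still lists all recorded transfusions, historical and on-study, with no product filter. Section 2 of the Part B SAP says that the earlier plan produced the interim Part A analysis and that the new plan governs the final analysis. Both plans cite the same protocol version, so no protocol change accounts for the difference.

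**The concern.** One endpoint has two operational definitions in two reports of the same trial. Whole blood contains red cells, and the Part A SAP treats it as an RBC transfusion. Under the Part B SAP as worded, a whole-blood transfusion adds nothing to the derived rates or units. A subject whose only transfusions were whole blood would be left out of the final summary table altogether, rather than appear with a lower rate.

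The overlap between the reports is mainly the pre-study baseline, which both derive. The Part A treatment period also overlaps: the interim report counts it with whole blood, and the final report counts it again, packed cells only, inside Part A + B. With at most 12 subjects per cohort, and only those who rolled over and received 1,080 mg in the final analysis sets, a single reclassified subject could show in a cohort mean.

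**Working it through.** Neither plan states a figure to reproduce, because the analyses are descriptive and the documents give no transfusion counts. The check applies each plan's own formulas to hypothetical counts of PRBC (k) and whole blood (w).

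**Inputs**

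- Part A SAP 5.3.1: baseline = (k + w)/12; on-study = (k + w) × 28/days.
- Part B SAP 5.3.1.1: baseline = k × 28/365; on-study = k × 28/days. Reading these counts as PRBC relies on the section title and lead-in, since the fractions themselves mention only transfusions.
- Part B SAP 5.1.3: baseline printed as k × 365/28.
- Duration: Part A runs to Day 336. The last windowed Part B visit is Part B Day 1176 (Part B SAP 4.2.3). A subject who switches at Day 336 and stays to that visit has about 336 + 1176 = 1512 days.

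**Pre-study baseline, per month**

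| k | w | Part A SAP | Part B SAP 5.3.1.1 |
|---|---|---|---|
| 0 | 1 | 1/12 = 0.083 | 0 |
| 5 | 1 | 6/12 = 0.500 | 5 × 28/365 = 0.384 |
| 6 | 0 | 6/12 = 0.500 | 6 × 28/365 = 0.460 |

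The second row's gap is 0.500 − 0.384 = 0.116. With the same products, the Part B formula gives 6 × 28/365 = 0.460. So 0.460 − 0.384 = 0.077 (one transfusion, 28/365) comes from dropping whole blood, and 0.500 − 0.460 = 0.040 comes from the month length. The third row has no whole blood and still differs: (28/365)/(1/12) = 0.921, which is 7.9% lower.

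**On-study rates in the final report**

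The final report gives Part A + B and Part B rates. Each omitted whole-blood transfusion lowers the rate by 28/days:

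- Part A + B, 1512 days: 28/1512 = 0.019.
- Part A + B, 336 + 672 = 1008 days (last visit at Part B Day 672): 28/1008 = 0.028.
- Part B alone, 1176 days: 28/1176 = 0.024.

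For example, 3 PRBC plus 1 whole blood over 1512 days gives 4 × 28/1512 = 0.074 with whole blood and 3 × 28/1512 = 0.056 without.

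**The factor in 5.1.3**

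Read literally, 6 PRBC in the year before dosing gives 6 × 365/28 = 78.2 per month, against 0.460 from 5.3.1.1 of the same plan. The factor is inverted.

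**The case against.** The strongest reply is that this is a labelling difference in exploratory, purely descriptive analyses. The Part B SAP has no sentence excluding whole blood. Within the final report the PRBC label applies to baseline and on-study periods alike, so its internal comparison does not mix definitions. The summary tables of the two reports would differ anyway: the interim report covers everyone dosed, by randomized dose within cohort, while the final report covers only subjects who rolled over and received 1,080 mg, by cohort. All of this stands, and it keeps the point low in priority. It does not explain why the count was narrowed while the endpoint stayed RBC transfusions, and subject-level baseline rates remain directly comparable between the reports.

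A reader might infer three stronger things that the documents do not support.

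- That whole-blood transfusions disappear from the final report. They do not, because the history and on-study listings are unfiltered. They leave only the derived rates and summary tables.
- That the two reports must show different values because of the product rule. That needs at least one whole-blood transfusion, and the documents report no counts.
- That an omitted transfusion costs 28/336 = 0.083 on study. That is its weight in a rate for Part A alone, which the final report does not derive. Over Part A + B the divisor is all the days in both parts.

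**Conclusion.** The inconsistency is real, unexplained and of low priority. As worded, the Part B SAP can undercount a named endpoint relative to the Part A SAP and can drop subjects who received only whole blood from its summary tables. Per historical whole-blood transfusion, the between-report difference in a subject's baseline is 1/12 = 0.083 per month. Per on-study one, the final rate falls by 28 divided by the days in the period, about 0.019 over 1512 days and more with shorter follow-up. If no whole blood was given, the product rule changes nothing.

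The conclusion rests on reading the PRBC headings and lead-ins as the counting rule, which 5.1.3 supports explicitly for baseline. It also rests on reading the table-membership rule in 5.3.1.4 as requiring a PRBC transfusion at baseline or afterwards.

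The product rule is not the only reason the baselines disagree. The month lengths differ for every subject with a transfusion history, so aligning the products alone would leave the baselines 7.9% apart.

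**What to change.** In Part B SAP 5.1.3 and 5.3.1, define the count as whole blood plus PRBC for every baseline and on-study rate, for units and for the table-inclusion rules, and re-title the tables as RBC transfusions. In the same edit:

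- Use one month length for the baseline in both reports. The factor 28/365 matches the 28-day month that both plans already use on study. As the interim tables were made with /12, the final report should say so where it shows the baseline.
- Correct the factor in 5.1.3 from 365/28 to 28/365.

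If the narrower count was intended, the final report should state and justify it, with the number of whole-blood transfusions left out.

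The cost is one definition line, two formula corrections and a change to a program filter. No new data are needed: the listings already cover all recorded transfusions, and the interim rule already required product type to be distinguished.

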# 12.1 Screening

Screening will begin within 30 days prior to dosing to confirm that subjects meet the subject selection criteria for the study. Informed consent will be obtained at screening (see Section 15.6.3). Subjects will have to meet all eligibility criteria before being enrolled into the study (see Section 10).

Subjects should not be rescreened once they have been designated as a screen failure, unless this is discussed in advance and documented in writing with the sponsor.

The following will be recorded at screening: ECG, vital signs, hematology, serum chemistry, urinalysis, serum pregnancy test, physical examination, medical history, including concomitant medications, and demographic data, including, sex, age, race, body weight (kg), height (cm).

Confirm sufficient supplementation of iron, folic acid and vitamin B12 prior to treatment phase, if not, subjects need to be treated with supplements for at least 3 weeks prior to study enrollment.

Medical history on hemoglobin level, and the number of RBC transfusions in the past year prior to study enrollment will be collected.

Treatment history of dose and duration will be collected such as steroids, and rituximab.

Subjects requiring alternative prophylactic antibiotics (Erythromycin 500 mg twice daily, or Azithromycin 500 mg 3 times per week) will initiate antibiotic treatment at least one week prior to first dose of APL-2. QTc interval is to be confirmed prior to dosing with APL-2.

Screening procedures are listed in the Study Flow Chart in Section 3.

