## 4.3 Test Hypothesis and *P*-Value Justification

No formal inferential statistics will be applied to data collected in this study.

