## 4.5 Interim Analysis

One interim analysis is planned when all subjects enrolled in the study have completed Part A, the Core Study Phase (screening to day 336) or discontinued prior to Day 336. The interim analysis will present all planned tables, listings, and figures (TLF) listed in Appendix 8.1 for only the Part A Core Study Phase. The data will consist of:

- For subjects who rollover into the Part B Extension Phase, all data collected through the date of Visit 15 will be included. For occurrence data, such as Adverse Events and Concomitant Medications, records with a start date on or before the Visit 15 (which is considered the start of dosing date for the extension phase) will be included.
- For all subjects who do not rollover into the Part B extension Phase (i.e. who discontinue during the Part A Core Study Phase), all data will be included.

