# 5. STATISTICAL ANALYSIS METHODOLOGY

In general, tables will be presented by cohort (Cohort 1 wAIHA / Cohort 2 CAD) and study part (Part A + B / Part B). The Part B summaries will start from Study Day 1 in Part B through the end of the Part B Long Term Extension Phase, while Part A + B will start from Study Day 1 in Part A through the end of the Part B Long Term Extension Phase.

Tabulations for continuous data will use a standard set of descriptive statistics for the results and for change from baseline, as specified: number of observations available (n), mean, standard deviation (SD), median, and range (minimum, maximum). Change from Baseline for Part A + B summaries will calculate the Change from Part A Baseline summary statistics. Change from Baseline for Part B summaries will calculate the Change from Part B Baseline summary statistics.

Categorical or dichotomous data will be tabulated using frequencies (counts and percentages). The numerator and denominator for each percentage calculation will be specified in the footnotes of table shells. Categorical data will be populated as appropriate for each study part (Part A + B and Part B).

Data listings will present all information recorded in eCRFs for all subjects and visits. All listings will be sorted by cohort and subject number.

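### Part A SAP 5.3.1 has no consistent date rule around the first dose, so a transfusion between screening and Day 1 may count in baseline, in Part A, or in neither

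*SAP*

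**What the plan says.** There are two SAPs: one for the Part A interim analysis (April 2020) and one for Part B and the whole study (November 2022).

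**Baseline, Part A SAP 5.3.1.** The rate is the "number of transfusions reported on 12-month transfusion history /12". Protocol 12.1 and 13.1.2 place collection of that history at screening: "the number of RBC transfusions in the past year prior to study enrollment will be collected". The flow chart schedules medical and treatment history at Visit 1 only. The same SAP section nevertheless defines the baseline subset as subjects with "at least 1 infusion in the 365 days prior to first study dose".

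**On study, Part A SAP 5.3.1.** The rate is the "number of transfusion reported during study part", times 28, over the "number of days in that part of study". Neither term has a first day. The section classes Part A as a post-baseline phase and treats Parts A and B together as on-treatment, running between the first and the last dose. That boundary is stated for the combined period only.

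**Extent of Part A elsewhere.** Part A SAP 4.5 times the interim analysis at the point when all subjects have "completed Part A, the Core Study Phase (screening to day 336") or discontinued earlier. The protocol synopsis, Section 11 and Section 15.3 also start Part A at screening. The SAP 4.1.2 window table lists Visit 1 (Day -30) under Part A.

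**Part B SAP.** Section 5 says that "Part A + B will start from Study Day 1 in Part A", and 5.3.1.1 computes the baseline rate as transfusions in the 365 days before first dose, times 28, over 365.

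**The concern.** Screening can last up to 30 days, and Protocol 12.1 requires at least three weeks of supplementation before enrolment for subjects short of iron, folate or B12. Subjects enter with haemoglobin below 11 g/dL, and no eligibility criterion bars a transfusion during screening. Such events are therefore plausible.

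The plan does not say where one belongs. A history form completed at Visit 1 need not contain it. The 365-day wording puts it in baseline. The screening-to-Day-336 wording, read literally, puts it in Part A. If Part A starts at first dose and the form is not updated, it is counted nowhere. A subject could even enter the baseline subset because of a transfusion that is missing from that subject's own baseline count.

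At stake are the change from baseline in transfusions and units, and the number of subjects with at least one transfusion in Part A. Adverse events and medications have explicit first-dose rules in the same SAP (5.1.4, 5.2.1). Transfusions, a listed efficacy endpoint, have none.

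**Working it through.** The plan states no numerical result to reproduce, so the check applies its formulas to the possible placements.

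**Inputs from the documents:** 336 treatment days in Part A (Protocol 12.4); screening of at most 30 days (Part A SAP 3.3); up to 6 subjects per dose group (protocol synopsis).

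**1. Effect of one pre-dose transfusion on the Part A rate** (count × 28 / days):
- Part A starts at first dose: adds 0.
- Part A starts at screening: 28/366 = 0.077 (30-day screening), 28/350 = 0.080 (14 days), 28/343 = 0.082 (7 days).
- Counted in the numerator only: 28/336 = 0.083.

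**2. Effect on a group of six.** The mean rate moves by 0.077/6 = 0.013 to 0.083/6 = 0.014. The subset with at least one transfusion can move by one subject, 1/6 = 17 percentage points.

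**3. One subject, three placements.** Assumed counts: 12 transfusions in the history, 1 in a 30-day screening, 2 on treatment.

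| Placement of the screening transfusion | Baseline (count/12) | Part A rate | Change |
|---|---|---|---|
| Baseline | 13/12 = 1.083 | 2×28/336 = 0.167 | -0.917 |
| Part A, starting at screening | 12/12 = 1.000 | 3×28/366 = 0.230 | -0.770 |
| Neither | 12/12 = 1.000 | 2×28/336 = 0.167 | -0.833 |

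The same record gives changes that differ by up to 0.917 - 0.770 = 0.147.

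**4. Units of the two rates.** Baseline is per calendar month (1/12 of a year) and the on-study rate is per 28 days. An unchanged yearly rate gives (28/365)/(1/12) = 336/365 = 0.921, an apparent fall of 7.9% with no change at all. This is separate from the date question but sits in the same formulas, so it should be corrected together with it.

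**5. Date-based rule on the same subject**, assuming that all 12 history transfusions also fall within 365 days of first dose: baseline 13×28/365 = 0.997, Part A 0.167, change -0.831. This lies close to the third row above only because a missing baseline event and the inflated /12 scaling happen to offset each other.

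**6. How often it could arise.** The documents give no transfusion rate. If transfusions were Poisson at an assumed 0.25, 0.5 or 1.0 per 28 days, the chance of at least one during screening, 1 - exp(-rate × days/28), would be 23%, 41% or 66% at the 30-day maximum, and 6%, 12% or 22% at 7 days. These are illustrations, not estimates for this population.

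**The case against.** A reader might infer that the Part A SAP counts transfusions given before any APL-2 as Part A events, and so charges them to the drug. The documents do not support that:

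- Section 5.3.1 classes Part A as post-baseline and the combined parts as on-treatment, and defines the baseline subset by the period up to first dose.
- The compliance rule in 5.1.5 sets expected daily doses equal to the days in Part A, which works only if Part A begins with dosing.
- The column heading of the protocol flow chart starts the Core Study Phase on Day 1, although the table's title starts at screening.
- Part B SAP Section 2 defines Part A as the period of the daily regimen.
- The screening-to-Day-336 wording in SAP 4.5 concerns the timing of the interim analysis, not transfusions. The window table assigns visits, not exposure time.

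Nor is it certain that the history form misses the event. The form covers the year before enrolment, and Protocol Section 9 enrols subjects on Day 1. Part B SAP 4.1, however, treats subjects as enrolled at consent, and whether the form is updated after Visit 1 depends on an eCRF that is not in these documents.

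The stakes are limited. The analysis is labelled exploratory, and "No formal inferential statistics will be applied to data collected in this study". Neither document names a transfusion-free endpoint, and all transfusions are listed, so a misplaced event could be found.

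Most of this stands, and it rules out the stronger claim. It does not supply the missing rule: first dose is the better inference for Part A but is not stated there, and the form-based baseline rate and the date-based baseline subset remain different rules.

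**Conclusion.** The point holds as an inconsistency of attribution. Part A SAP 5.3.1 takes the baseline rate from a form completed at screening, defines the baseline subset by the year before first dose, and sets no first day for Part A. The documents do not show that pre-drug transfusions are counted against APL-2, nor that the result is biased in a known direction.

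The size is about 0.08 per 28 days for each transfusion placed in Part A, and possibly one subject in the at-least-one subset of a group of up to six. These figures assume the event occurs and is placed in Part A; how often that would happen cannot be determined from the documents. The 7.9% scaling difference does not depend on the placement question.

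The correction is worth making because it replaces a form-based rule with a date-based one, and the Part B SAP already uses those dates. That plan cannot repair the Part A results for everyone, since its analysis sets include only subjects who received 1,080 mg.

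**What to change.** In Part A SAP 5.3.1, attribute transfusions and units by date:

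- **Baseline:** all transfusions dated in the 365 days before the first APL-2 dose, from the history form plus any screening-period records. Scale by 28/365, as in Part B SAP 5.3.1.1 and 5.3.1.2, so that baseline and on-study rates share the 28-day unit.
- **Part A:** numerator, denominator and the subset with at least one transfusion all start on Study Day 1.
- **Baseline subset:** defined from the same dated records as the baseline rate.

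The cost is a short change of wording, a date filter and a changed scaling factor. One check is needed first: neither document states that transfusions between the screening visit and Day 1 are captured with dates, so eCRF capture should be confirmed. If those records exist, no new assessment is required.

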## 2. INTRODUCTION

This Statistical Analysis Plan (SAP) is prepared to provide a more technical and detailed elaboration of the principal statistical features stated in the protocol. The SAP will ensure that the tables, listings, and figures that will be produced and statistical methods that will be used for the final analysis are complete and accurate and will allow valid conclusions to be drawn.

In the development of this final analysis SAP, the following study documents were used:

- Protocol Number (Version 1.0 Amendment 4), 17 Jan 2019
- Electronic Case Report Form (eCRF), extracted 18 Oct 2021
- Medical Coding Guidelines (Version 5.0), 10 Sep 2021

The study protocol consists of two study parts for analysis (details of the scheduled assessments of the study parts can be found in Section 3.3 of the SAP):

- Core Study Phase (Part A): the study period of the daily 270/280 mg or 360 mg APL-2 dose regimen.
- Long Term Extension Phase (Part B): the study period of the twice or three times weekly 1080 mg APL-2 dose regimen.

Statistical Analysis Plan Version 1.0 was used for the production of the Interim Part A Core Study Phase Analysis. This SAP will present the results for the final analysis for subjects who rolled over into Part B, presenting the safety and efficacy results of Part B and Part A + B as whole completed study as well. Definitions for the study days and baselines are outlined in Section 4. Details of the planned analyses are outlined in Section 5.

In the event that a discrepancy is found between the descriptions in the statistical section of the protocol and this document, the description in this document supersedes the descriptions in the statistical section of the protocol. Any deviations from the final analysis plan or from what is outlined in the protocol will be discussed in the final study report.

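### Transfusion rates: the Part A SAP subtracts a calendar-month baseline from a 28-day on-study rate (a false fall of 7.95% of baseline), and the Part B SAP inverts a conversion factor in its baseline table

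*SAP*

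**What the plan says.** There are two SAPs: one dated 27 Apr 2020, used for the Part A analysis, and one dated 08 Nov 2022 for the Part B extension and the final analysis.

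**Part A SAP, 5.3.1.** The on-study rate takes the "number of transfusion reported during study part", multiplies it by 28 and divides by the days in that part. A sentence after this formula says units are handled similarly. Baseline comes next and is treated differently: "The baseline number of transfusions per month will be calculated as number of transfusions reported on 12-month transfusion history /12". That sentence names transfusions only. The baseline look-back is 365 days, since the baseline summary is for subjects "who had at least 1 infusion in the 365 days prior to first study dose". The two rates are then brought together as "Change from Baseline of the Number of Transfusions and Units for the N subjects in the dose group".

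**Part B SAP, 5.3.1.1 and 5.3.1.2.** Baseline is the number "of transfusions in 365 days prior to first APL-2 dose" times 28/365. Units use the number "of units in 365 days prior to first APL-2 dose" times 28/365. On-study rates are count x 28/days, so both sides use a 28-day month.

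**Part B SAP, 5.1.3.** The baseline-characteristics row for monthly transfusions before first dose is "derived as the number of Packed Red Blood Cell transfusions in the 365 days prior to first APL-2 dose", followed by *365/28.

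The Part B SAP Introduction adds that "Statistical Analysis Plan Version 1.0 was used for the production of the Interim Part A Core Study Phase Analysis".

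**The concern.** Dividing a yearly count by 12 gives a valid rate per calendar month of about 30.4 days. Scaling to 28 days is equally valid. Subtracting one from the other is not, because the longer baseline month holds more transfusions at the same underlying rate.

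The number of RBC transfusions is a listed efficacy endpoint. The study is open label and both dose groups receive APL-2, so the efficacy reading for transfusions rests on change from each subject's own history. The error always runs in the favourable direction and is zero only for subjects with no transfusions in the prior year.

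The consistent formulas in the Part B SAP do not repair the Part A result. The Part B ITT Set holds only subjects who rolled over and received at least one 1,080 mg dose, whereas the Part A ITT Set holds everyone dosed. The transfusion change in all dosed subjects is therefore defined only by the mismatched rule. A rollover subject also has two different baseline rates in two reports of one study.

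The Part B 5.1.3 factor is a separate slip: an inverted fraction that contradicts 5.3.1.1 of the same document.

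**Working it through.** Neither SAP states a resulting figure, so there is none to reproduce. The inputs are the formulas above: baseline count / 12 over 365 days and on-study count x 28/days (Part A SAP 5.3.1); count x 365/28 (Part B SAP 5.1.3); count x 28/365 (Part B SAP 5.3.1.1).

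**(a) Part A, unchanged rate.** Let the daily rate be L before and during the study.

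- Baseline as written: 365L/12 = 30.42L
- On study as written: 28L
- Ratio: 28 x 12/365 = 336/365 = 0.9205
- False fall: 1 - 0.9205 = 0.0795, or 7.95% of the baseline rate

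For y transfusions in the prior year, the false fall per month is y/12 - 28y/365. The values of y are assumptions, because the documents give no transfusion frequency.

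| y per year | Baseline, y/12 | Same rate on study, 28y/365 | False fall per month |
|---|---|---|---|
| 2 | 0.167 | 0.153 | 0.013 |
| 6 | 0.500 | 0.460 | 0.040 |
| 12 | 1.000 | 0.921 | 0.079 |
| 24 | 2.000 | 1.841 | 0.159 |

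Two further cases at 12 per year:

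- True halving: on study 6 x 28/365 = 0.460. The fall shown is 1.000 - 0.460 = 0.540; on one basis it is 0.921 - 0.460 = 0.460.
- No transfusions on study: the fall shown is 1.000; on one basis it is 0.921.

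The result depends little on the length assumed for the year: 8.01% with 365.25 days, 8.20% with 366 and 6.67% with 360. It vanishes only if the 12-month history covered 336 days (12 x 28). The protocol does label the 336-day core phase as 12 months, but the history it collects (Protocol 12.1) covers the past year, and Part A SAP 5.3.1 says 365 days.

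**(b) Part B SAP 5.1.3 against 5.3.1.1.**

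- Factor as written: 365/28 = 13.04
- Factor in 5.3.1.1: 28/365 = 0.0767
- Ratio: (365/28)^2 = 169.9
- 12 per year: 12 x 365/28 = 156.4 per month instead of 12 x 28/365 = 0.92
- 2 per year: 26.1 instead of 0.15

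**The case against.** The case for leaving this alone, or treating it as trivial, is as follows.

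- **The percentage is not a planned output.** Part A SAP 5.3.1 asks for absolute values and change in transfusions, whereas FACIT, LASA and the laboratory endpoints also get percent change. This stands. The 7.95% is a scaling factor; what the tables would show is the absolute difference above.
- **Units may be covered.** The sentence on a similar calculation for units could be read as including baseline. It follows the on-study formula and comes before the division by 12, so a programmer could reasonably choose either basis. The baseline rule for units is not explicit.
- **The consequence is limited.** The analysis is exploratory, with no inferential statistics and up to 6 subjects per dose group in each cohort. Both dose groups use the same formula, and the raw history and on-study transfusions are listed, so rates can be recomputed. All true. These points limit the harm but do not make the comparison valid.
- **The final analysis is already consistent.** This is true for Part B and Part A + B, but only in subjects who rolled over.
- **The 5.1.3 factor is an obvious inversion.** A value of 156 per month would probably be caught in quality control. Agreed; on its own it is minor.
- **Month length is not the only difference.** Part A counts whole blood and packed cells, Part B packed cells only. A subject with whole-blood history would still have two baseline counts after the fix. This is a separate matter that the month length neither causes nor cures.

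**Conclusion.** Both formulas are wrong as written. In the Part A SAP an unchanged transfusion rate appears as a fall of 7.95% of the baseline rate, given the 365-day look-back stated in the same section. In absolute terms that is 0.013 to 0.159 per month over an assumed 2 to 24 transfusions a year. It is modest, but it favours treatment whenever there is a transfusion history. On-study rates, the other efficacy endpoints and the Part B SAP's own efficacy formulas are unaffected, and no test or sample size depends on it.

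In the Part B SAP the error is confined to one descriptive row.

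The first should be fixed, because it concerns a named endpoint and outputs may already carry it. The second is a one-line correction. Whether the Part A programs actually divided by 12 cannot be told from the documents.

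**What to change.** - **Part A SAP 5.3.1:** replace the baseline sentence with: *Baseline transfusions per month = number of transfusions in the 365 days before first dose x 28/365; baseline units per month = number of units in the same 365 days x 28/365.* This puts the month length on the same basis as Part B SAP 5.3.1.1 and 5.3.1.2.
- **Part A outputs:** check the transfusion tables and the per-month listing. If they divided by 12, re-run them and re-issue with a note in the report.
- **Part B SAP 5.1.3:** change *365/28 to *28/365.

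The cost is two wording changes, two one-line program changes and the check of existing outputs. If division by 12 was used, each subject's absolute Part A reduction will shrink by 7.95% of the reported baseline rate (0.079 per month for 12 transfusions a year).
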